10.5 Final Analysis Plan

10.5.1 General Considerations

The SAP, which includes more technical and detailed elaboration of the principal features stated in the protocol, will be prepared separately and finalized before the interim analysis.

Safety will be assessed by estimating the occurrence of Grade 2 or higher treatment-emergent AEs in the IV bacteriophage therapies compared to placebo through Day 30 ± 7 days.

Microbiological activity will be assessed by estimating changes in $\log_{10} P. aeruginosa$ CFU/mL (total and each morphology) in sputum cultures from baseline through Day 30 ± 7 days.

The benefit to risk profile will be assessed by comparing the DOOR of IV bacteriophage arms and placebo arm through Day $8 + 3$ days. The DOOR will be analyzed by estimating the DOOR probability (Section 10.5.5), (i.e., the probability of a randomly selected subject having a better DOOR if assigned to receive an IV bacteriophage therapy compared to placebo).

All statistical calculations will be performed using up-to-date versions of SAS version 9.4 or higher (SAS Institute Inc., Cary, NC, USA) or language and environment for statistical computing 3.6.1 or higher (R Foundation for Statistical Computing, Vienna, Austria), unless otherwise specified. All PK analyses will be performed using NONMEM version 7.3 or higher (ICON Development Solutions, [name]). For continuous variables, summary statistics will include sample size, mean, SD, median, quartiles, minimum, and maximum values. Frequencies and percentages will be calculated for categorical variables. All reported confidence intervals will be two-sided 95%. Graphical displays will be produced.

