### 3.3. Study Definitions and Derived Variables

#### 3.3.1. Definitions for the DOOR Endpoint

Most desirable	Rank 1	No SAE (related to study product) and $> 2 \log_{10}$ reduction in P. aeruginosa CFU/mL
↑	Rank 2	No SAE (related to study product) and $1-2 \log_{10}$ reduction in P. aeruginosa CFU/mL
↓	Rank 3	No SAE (related to study product) and $< 1 \log_{10}$ reduction in P. aeruginosa CFU/mL
Least desirable	Rank 4	SAE (related to study product)

Abbreviations: CFU: colony-forming units; mL: milliliter; SAE: serious adverse events.

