- Cumulative proportions of DOOR categories through Day 8 + 3 for IV bacteriophage vs. placebo with cumulative DOOR probabilities and corresponding 95% CI ([Table 31](#)). This analysis compares the DOOR probability from the following dichotomizations of DOOR: first by calculating the dichotomized DOOR probability comparing those with DOOR rank = 1 to DOOR ranks 2, 3, and 4 pooled together, then DOOR rank 1 and 2 compared to DOOR rank 3 and 4, and finally comparing DOOR ranks 1, 2, and 3 to DOOR rank 4.
- Sequential dichotomization of DOOR will be presented in [Figure 12](#). Cumulative probabilities will be calculated using the following dichotomizations: rank 1 vs ranks 2, 3, and 4; ranks 1 and 2 vs ranks 3 and 4; and ranks 1, 2, and 3 vs rank 4.
- Comparison of each of the components of the DOOR between the IV bacteriophage and placebo arms through Day 8 with 95% CI, summarized by DOOR probability and 95% CI ([Table 33](#)). For the SAE component of DOOR the dichotomized DOOR probability will be calculated using ‘No SAE’ = rank 1 and ‘SAE’ = rank 2. For the log10 reduction component of DOOR the dichotomized DOOR probability will be calculated using ‘>2 log10 reduction in *P. aeruginosa* CFU/mL’ = rank 1, ‘1-2 log10 reduction in *P. aeruginosa* CFU/mL’ = rank 2, and ‘<1 log10 reduction in *P. aeruginosa* CFU/mL’ = rank 3.
- Forest plot of probabilities of DOOR and its components at Day 8 + 3 and corresponding 95% CI calculated using the method in Halperin et. al. [2] ([Figure 10](#)).
- Point estimate and CI of difference in mean partial credit vs. placebo through Day 8 and corresponding 95% CI ([Table 32](#)). The 95% CI will be calculated using Welch’s t-test. The partial credit analysis will be calculated assigning a grading key to each of the DOOR categories. The grading keys used will be the following: A: (DOOR rank 1 = 100, rank 2 = 100, rank 3 = 100, rank 4 = 0), B: (rank 1 = 100, rank 2 = 100, rank 3 = 0, rank 4 = 0), C: (rank 1 = 100, rank 2 = 0, rank 3 = 0, rank 4 = 0). For each scenario, the mean and SD of these partial credit scores will be provided for each treatment group and corresponding scenario.
- Difference in means of partial credit score by time point ([Figure 13](#)).

A listing of individual DOOR response data will be presented in [Listing 12](#).

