**Table 32: Difference in Mean Partial Credit for DOOR Categories Through Day 8 – ITT Population, Stage 2a and 2b**

[Implementation note: ‘Selected IV Bacteriophage Dose’ will be replaced with the dose chosen by the interim analysis. The 95% CI for the difference in means is computed from Welch’s t-test]

Scenario	Time Point	Treatment Group	n	Mean (SD)	Difference in Means (95% CI) a
A: (1=100, 2=100, 3=100, 4=0)	Day 1 Post-infusion	Selected IV Bacteriophage Dose (N=X)	xx	xx (xx.x)	xx (xx.x, xx.x)
		Placebo (N=X)	xx	xx (xx.x)	
	Day 2	Selected IV Bacteriophage Dose (N=X)	xx	xx (xx.x)	xx (xx.x, xx.x)
		Placebo (N=X)	xx	xx (xx.x)	
	Day 5	Selected IV Bacteriophage Dose (N=X)	xx	xx (xx.x)	xx (xx.x, xx.x)
		Placebo (N=X)	xx	xx (xx.x)	
	Day 8	Selected IV Bacteriophage Dose (N=X)	xx	xx (xx.x)	xx (xx.x, xx.x)
		Placebo (N=X)	xx	xx (xx.x)	
	Maximum	Selected IV Bacteriophage Dose (N=X)	xx	xx (xx.x)	xx (xx.x, xx.x)
		Placebo (N=X)	xx	xx (xx.x)	

[Extend the table to add Scenarios B: (1=100, 2=100, 3=0, 4=0) and C: (1=100, 2=0, 3=0, 4=0)]

Notes: N=Number of subjects in the ITT population in Stage 2a and 2b.

n=Number of subjects in the corresponding analysis population with non-missing values of partial credit scores.

SD=Standard Deviation.

aThe 95% CI for the difference in means is computed from Welch’s t-test.

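### Key A of the partial-credit analysis puts a Welch interval on a related-SAE indicator, so its confidence interval collapses to zero width, or cannot be computed, if neither arm has a related SAE

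*SAP*

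**What the plan says.** SAP 8.1.3 includes, among the DOOR analyses, a difference in mean partial credit between the selected dose and placebo. Protocol 10.5.5 and its Table 3 list the same analysis. The SAP text gives three grading keys. The one at issue is "A: (DOOR rank 1 = 100, rank 2 = 100, rank 3 = 100, rank 4 = 0". Key B gives full credit to the two best ranks and none to the other two; Key C gives full credit to the best rank alone. No key assigns anything between 0 and 100.

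The interval method is also fixed in that section: "The 95% CI will be calculated using Welch’s t-test". The Table 32 shell shows Key A as "A: (1=100, 2=100, 3=100, 4=0" and again names Welch's method for the interval. Key A is tabulated at Day 1 post-infusion, Days 2, 5 and 8, and for the maximum. The later SAP addendum on undetectable colony counts keeps the keys and the method unchanged in its Tables 24 and 25.

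SAP 3.3.1 defines Rank 4 as "SAE (related to study product". No passage says what to report when the scores have no variance.

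**The concern.** Ranks 1 to 3 all score 100 under Key A and only Rank 4 scores 0. The mean score in an arm is therefore 100 times the proportion free of a related SAE, and the difference in means is a risk difference in percentage points. Welch's interval takes its width from the sample SDs. When an event is rare enough that none is seen in either arm, both SDs are 0 and the width disappears.

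What is at stake is a safety contrast printed as 0 (0, 0), or as an empty cell, with 20 to 25 subjects per arm. A zero-width interval invites the reading that a difference in related SAEs has been excluded. With that many subjects the data leave a wide range open.

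**Working it through.** **Inputs.** Keys and interval method: SAP 8.1.3 and Table 32. Subjects per arm: 20 to 25 (SAP 5). Level: "All reported confidence intervals will be two-sided 95"% (Protocol 10.5.1). Related-SAE rate: the documents give none; Protocol 2.3.1 says only that none has been published. The rates below are my assumptions, shown over a range.

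**The plan's own figure.** The plan states no precision for the partial-credit analysis. Its only precision figure is 51% to 89% for a DOOR probability of 70% at 20 per arm. With the Wilcoxon null variance, 0.70 ± 1.96 × √[41/(12 × 20 × 20)] gives 51.9% to 88.1%, within about a point of it. That figure does not bear on Key A.

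**Step 1: Welch on Key A with no event in either arm.** SE = √(s₁²/n₁ + s₂²/n₂) = √(0 + 0) = 0, so the difference is 0 and the interval is (0, 0) at any n. The Welch degrees of freedom are 0/0. Run in practice, Python's scipy returns (0, 0). R's t.test stops with an error that the data are constant, and R is one of the two packages named in SAP 14.

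**Step 2: one event restores a width.** With one related SAE in the phage arm at n = 20, that arm has mean 95 and SD 22.36, so SE = 22.36/√20 = 5. With 19 df the difference is −5 (−15.5 to 5.5). At n = 25 it is −4 (−12.3 to 4.3). The collapse requires no event in either arm.

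**Step 3: how likely that is.** P(no event) = (1 − p)^(2n) at a common rate p:

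| Assumed rate | 40 subjects | 50 subjects |
|---|---|---|
| 0.5% | 82% | 78% |
| 1% | 67% | 61% |
| 2% | 45% | 36% |
| 5% | 13% | 8% |

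**Step 4: what the data would support.** For 0/n against 0/n the constrained estimates at a difference d are d and 0. The Miettinen-Nurminen limit then solves [d/(1 − d)] × (2n − 1)/2 = 3.84.

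- n = 20: d/(1 − d) = 7.68/39 = 0.197, so d = 16.5 points.
- n = 25: d/(1 − d) = 7.68/49 = 0.157, so d = 13.6 points.

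Newcombe's interval gives ±16.1 and ±13.3.

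**Step 5: the SAP's other interval for the same contrast.** Tables 31 and 33 use the Halperin formula of SAP 8.1.3. With no event at n = 20, θ = 0.9972, γ = 39 − 38 × 0.9972 = 1.105, and C = 1.105 × 3.84/400 = 0.0106. The DOOR probability is 0.50 (0.449 to 0.551). For a two-category outcome the risk difference is 2 × (DOOR probability − 0.5), so this is about ±10 points. At n = 25 it is 0.459 to 0.541, about ±8 points.

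**Step 6: coverage of the Welch interval under Key A** (exact binomial enumeration, assumed rates).

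- 2% against 0%: the interval has zero width, and so misses, with probability 0.98²⁰ = 0.67 at n = 20 and 0.98²⁵ = 0.60 at n = 25. Coverage is 33% and 40%.
- 5% against 0%: coverage is 64% and 72%.
- Equal rates, n = 20: 100.0% at 1%, 99.9% at 2%, 98.8% at 5%. Here the zero-width interval counts as covering because it sits exactly on the true difference of 0.

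**Step 7: Keys B and C.** With assumed proportions scoring 100 of 30% against 10%, Welch coverage is 94.4% (n = 20) and 95.2% (n = 25). At 20% against 5% it is 93.7% and 94.7%. At 10% against 5% it is 91.9% and 91.6%.

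**The case against.** The strongest reply is that the contrast is already reported properly. Table 33 analyses the SAE component and Table 31 compares Ranks 1 to 3 with Rank 4, both with a Halperin interval that does not collapse. Tables 28 and 40 count related SAEs by arm. Table 32 is a supporting display, Key A is one of its three keys, no formal hypothesis test is planned (Protocol 10.1), and no decision rule uses the table. All of this stands, and it limits the consequence. It does not make the Table 32 entry right: the same comparison would carry about ±10 points in one table and ±0, or nothing, in another.

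A second reply is that the cell would explain itself, since the mean and SD beside it would read 100 (0.0) in both arms, and that R would print no interval at all. That is fair. The result depends on software, so it cannot be said that the report will claim certainty.

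A third reply is that the poor coverage figures fix placebo at 0%. That also stands. At equal rates coverage exceeds nominal, and the documents support no particular rate.

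A reader might infer two further things that the documents do not support. One is that Welch is wrong for the whole partial-credit analysis; Step 7 shows that it is adequate for Keys B and C unless proportions are sparse. The other is that no intermediate credit is planned at all. The three listed keys are indeed dichotomies, but the axis labels for Figure 13 refer to credit for Rank 2 and Rank 3, and the plot itself is not visible in the text available. There is no basis for requiring an additional key.

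**Conclusion.** The point holds for Key A. As written, the rule gives a zero-width or non-computable interval whenever neither arm has a related SAE by the time point among subjects with a DOOR rank. Under assumed common rates of 0.5% to 2%, that happens in 45% to 82% of trials with 40 subjects and 36% to 78% with 50. The interval that should stand there is about ±16.5 points at 20 per arm and ±13.6 at 25 by Miettinen-Nurminen.

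The zero-width result rests on the keys alone. The probabilities and coverage figures rest on assumed SAE rates.

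It would go too far to call this a wrong error bar on the primary benefit-risk result. The DOOR probability in Table 26 (addendum Table 14) is untouched, and the SAE contrast is bounded elsewhere. This is a defect in one supporting display that disagrees with the SAP's own other tables.

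**What to change.** In SAP 8.1.3, Table 32, and addendum Tables 24 and 25, replace Welch's t-test for Key A with the Miettinen-Nurminen interval for a difference in proportions, multiplied by 100 to stay on the score scale. The footnote of Table 45 already names this method, and Table 37 uses it too. Apply it to Keys B and C as well, so that one method serves all the 0/100 keys; for those keys the reason is consistency, plus protection when proportions are sparse.

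The point estimates do not change. The cost is one sentence in the text, three footnotes (with the matching implementation notes), and a small programming change using a method already needed for Table 45. No data, sample size or additional grading key is involved.

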#### 8.1.3.1. Intention-to-Treat (ITT) Analysis of DOOR using Inverse Probability Weighting

Intention-to-treat analysis requires that all randomized subjects be included in the analysis. However, missing data is prone to happen in clinical trials due to missing scheduled visits or loss to follow-up for example. In this case, analysis that is only based on complete data may be biased if the excluded subjects are systematically different from those included. IPW is one approach commonly used to reduce this bias under a MAR assumption. This is achieved by weighting complete cases with the inverse of their probability of being a complete case. While subjects missing the DOOR are excluded from the analysis per se, they may still inform the fitting of the logistic regression model used to provide predictions of the probability of completeness which are used to calculate the weights.

Specifically, let  $Y_i$  represent the outcome of interest (DOOR),  $X_i$  represent the covariates of interest,  $Z_i$  represent any other variables measured in the data but not used in the analysis model. For the IPW approach, we first define the missingness model to estimate the weights ( $w_i$ ) using a logistic regression model with outcome  $L$  and covariates taken from set  $(X, Z)$  where  $L_i$  is defined as 1 if DOOR data is complete (not missing) and 0 otherwise. Through this model, we obtain the fitted probabilities of each subject being complete, denoted as  $\pi_i$ .

The DOOR probability can then be calculated using DOOR at Day 8 as the outcome following the algorithm below:

1. Name DOOR from the group that received placebo “sample 1” and the DOOR score ranks from the group that received IV bacteriophage “sample 2”. Rename weights from sample 1 as  $w_{1i}$  and weights from sample 2 as  $w_{2i}$ .
2. Take the first observation in sample 2. If an observation in sample 2 has a smaller DOOR score rank than an observation in sample 1, then that observation in sample 2 gets an indicator of value of 1. Otherwise, if the observation in sample 2 is equal to the observation in sample 1, the observation in sample 2 gets an indicator value of  $\frac{1}{2}$ .
3. Let  $\pi_{1i}$  be the fitted probability of being complete for each observation in sample 1 and  $\pi_{2i}$  be the fitted probability for being complete for each observation in sample 2 obtained from the logistic regression model with an indicator for having non-missing DOOR score rank as the outcome.
4. For each pair in step 2, create the weight  $w_j$  as the inverse of the probability of both values in the pair being non-missing, i.e.,  $w_j = 1 / (\pi_{1i} \times \pi_{2i})$  with  $j$  being the index for observations in sample 2
5. For each pair in step 2, create the weighted indicator value as  $w\_ind_j = w_j \times indicator_j$
6. Repeat step 2 through 5 for all observations in sample 2.
7. The DOOR probability can then be obtained by  $DOOR\_prob\_IPW = \text{weighted average of all the indicator values in step 5}$ , i.e.;  $DOOR\_prob\_IPW = \frac{\sum_j w\_ind_j}{\sum w_j}$ ,

The DOOR probability (i.e.,  $\text{Pr}(\text{more desirable DOOR in IV bacteriophage}) + 0.5 \text{ Pr}(\text{Equal DOOR})$ ) using IPW is given by the value in  $DOOR\_prob\_IPW$ .

To estimate the 95% CIs for the DOOR probability, the approach discussed in Halperin et al. [2] after incorporating IPW weights is utilized. The superiority of IV bacteriophage vs placebo is concluded if the lower bound of the 95% CI for the DOOR probability is larger than 50%.

IPW will be used to handle missing data for the primary analysis of the DOOR endpoint. Percentage of subjects with missing DOOR data will be presented by time point and treatment group in [Table 25](#).

A tipping point analysis will be performed to estimate the impact of missing data on the primary analysis of the DOOR ([Table 27](#)).

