3.3 Study Endpoints or Outcome Measures

3.3.1 Primary

- Number of grade 2 or higher treatment-emergent AEs through Day 30 ± 7 .
- Change from baseline to Day 30 ± 7 days in \log_{10} *P. aeruginosa* total colony counts in quantitative sputum cultures after administration of IV bacteriophages/placebo.
- Desirability of Outcome Ranking (DOOR) using the greatest reduction by Day $8 + 3$ days Follow-up Visit.

More desirable	Rank 1	No SAE (related to study product) and $> 2 \log_{10}$ reduction in P. aeruginosa CFU/mL
↑	Rank 2	No SAE (related to study product) and $1-2 \log_{10}$ reduction in P. aeruginosa CFU/mL
↓	Rank 3	No SAE (related to study product) and $< 1 \log_{10}$ reduction in P. aeruginosa CFU/mL
Less desirable	Rank 4	SAE (related to study product)

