### **3.2. Endpoints**

#### **3.2.1. Primary**

- Number of Grade 2 or higher treatment-emergent AEs through Day  $30 \pm 7$ .
- Change from baseline to Day  $30 \pm 7$  in  $\log_{10}$  *P. aeruginosa* total colony counts in quantitative sputum cultures after administration of IV bacteriophages/placebo.
- Desirability of Outcome Ranking (DOOR) using greatest reduction by Day  $8 + 3$  follow-up visit.

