## 4.5. Primary Endpoint Variables

The three primary objectives are as follows: (1) the safety of a single dose of IV bacteriophage therapy in clinically stable CF subjects with *P. aeruginosa* in expectorated sputum, (2) the microbiological activity of a single dose of IV bacteriophage therapy in clinically stable CF subjects with *P. aeruginosa* in expectorated sputum, and (3) the benefit to risk profile of a single dose of IV bacteriophage therapy in clinically stable CF subjects with *P. aeruginosa* in expectorated sputum.

The safety endpoint will be measured by the number of Grade 2 or higher treatment-emergent AEs through Day  $30 \pm 7$ . Safety will also be assessed through the incidence of treatment-emergent adverse events (TEAEs), on-therapy SAEs, and AEs leading to premature discontinuation. Adverse events will be graded according to the Common Terminology Criteria for Adverse Events (CTCAE) Version 5.0, November 2017 ([https://ctep.cancer.gov/protocoldevelopment/electronic\\_applications/ctc.htm#ctc\\_50](https://ctep.cancer.gov/protocoldevelopment/electronic_applications/ctc.htm#ctc_50)). Details about adverse event grading and determination of relationship to study product can be found in the protocol, Section 8.1.1.1.

Clinical laboratory results, including chemistry, hematology, and liver function tests, will also be graded according to the CTCAE scale. Clinical chemistry parameters include serum creatinine, blood urea nitrogen (BUN), glucose, sodium, potassium, chloride, bicarbonate, and calcium. Hematology parameters include complete blood count with red blood cell (RBC) count, hemoglobin, hematocrit, total white blood cell (WBC) count with differential counts, and platelet count. Liver function tests include aspartate aminotransferase (AST), alanine aminotransferase (ALT), alkaline phosphatase, total bilirubin, lactate dehydrogenase, albumin, and total protein. Only AST, ALT, and total bilirubin are collected at Screening. Clinical chemistry, hematology, and liver function tests will be performed at baseline and at follow-up visits occurring on Days 2, 5, 8, 12 (Stage 1 only), and 30. Refer to Section 3.3.2 for the definition of baseline.

The microbiological activity endpoint will be measured based on the change in  $\log_{10}$  *P. aeruginosa* colony counts after administration of IV bacteriophages/placebo. Sputum collection for measuring colony counts will occur at baseline and at follow-up visits occurring on Days 2, 5, 8, and 30.

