## 6.5. Missing Data

While all efforts will be made to minimize missing data, some missing data is expected. Whenever possible, subjects terminating from the study early will be given an early termination (ET) visit during which the available components of DOOR and related measures can be recorded. A sensitivity analysis of DOOR will be performed using inverse probability weighting (IPW) to reduce the bias in DOOR outcome caused by missing data, assuming a missing at random (MAR) model (see [Section 8.1.3.1](#)). No other endpoints will be analyzed using techniques for missing data.

The effect that any missing data might have on results will be assessed via the inclusion of the IPW sensitivity analysis.

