### 8.2.4. Subgroup Analyses

A subgroup analysis of the primary endpoints will be conducted to explore whether estimated treatment effects vary significantly between subcategories of trial subjects, including bacteriophage susceptibility and presence of co-infection with other organisms recovered on sputum cultures. Analysis of the difference in

mean change between IV bacteriophage and placebo arms and the  $\log_{10}$ -transformed difference in mean change, along with the corresponding 95% CIs, will be presented by subgroup in [Table 22](#). A forest plot of the differences in *P. aeruginosa* colony counts is presented by subgroup in [Figure 8](#) and a forest plot of differences in the  $\log_{10}$  *P. aeruginosa* colony counts is presented by subgroup in [Figure 9](#). Analysis of the primary DOOR endpoint at Day 8 will be presented by subgroup in [Table 29](#) and a contingency table of DOOR by subgroup, treatment group, and time point will be presented in [Table 30](#). A forest plot of DOOR probability in subgroups will be presented in [Figure 11](#).

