**Figure 10: Forest Plot of Probabilities of DOOR Components at Day 8 – ITT Population**

**Figure 11: Forest Plot of DOOR Probability at Day 8, Subgroup Analysis – ITT Population**

[figure not shown]
**Figure 12:** Forest Plot of Sequential Dichotomization of DOOR Categories with 95% CI

[Implementation note: This figure will have one panel for Day 2, Day 5, and Day 8.]

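### SAP 8.1.3.1 runs the weighted DOOR algorithm on Day 8 DOOR while the endpoint is the greatest reduction by Day 8, and the SAP labels that weighted analysis both primary and sensitivity

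*SAP*

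**What the plan says.** **Outcome.** Protocol 3.3.1 defines the third primary endpoint as "Desirability of Outcome Ranking (DOOR) using the greatest reduction by Day" 8 + 3, and SAP 3.2.1 agrees. The first item in the SAP 8.1.3 analysis list, which produces Table 26, also uses the greatest reduction by Day 8. In SAP 8.1.3.1, however, the sentence that opens the weighted algorithm reads "The DOOR probability can then be calculated using DOOR at Day 8 as the outcome following the algorithm below".

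**Role of IPW.** SAP 6.5 states "A sensitivity analysis of DOOR will be performed using inverse probability weighting (IPW) to reduce the bias in DOOR outcome caused by missing data". SAP 8.1.3 first says IPW will handle the missing data, then in the next sentence assigns it to the sensitivity analysis. SAP 8.1.3.1 states "IPW will be used to handle missing data for the primary analysis of the DOOR endpoint".

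**Decision rule.** SAP 8.1.3 and 8.1.3.1 conclude superiority when the lower 95% limit for the DOOR probability exceeds 50%. Table 26 has one column with IPW and one without. Footnote b, which carries this rule, is attached to both, and neither is marked primary.

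**Addendum on undetectable counts.** It makes substitution at the detection limit primary and undetectable-as-missing the sensitivity analysis, then returns to the SAP's methods. Its Tables 14 and 15 repeat the two-column layout. It does not settle the role of IPW.

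**The concern.** A programmer working from 8.1.3.1 would score one sample per subject, the one from the Stage 2 virtual visit, where the endpoint takes the best of several. The ranks would change, and so would the completeness indicator that drives the weights.

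The role conflict is independent of this. With two columns under one superiority rule and no primary label, the reported primary result can be chosen after both are known. Stage 2a data have already been reviewed unblinded for dose selection, so the choice should be fixed in writing before the final analysis.

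**Working it through.** **1. The places side by side**

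| Place | Outcome scored | Role given to IPW |
|---|---|---|
| Protocol 3.3.1; SAP 3.2.1 | greatest reduction by Day 8 + 3 | none stated |
| SAP 6.5 | none stated | sensitivity |
| SAP 8.1.3, text before the list | none stated | handles missing data, then sensitivity |
| SAP 8.1.3, first list item | greatest reduction by Day 8 | none stated |
| SAP 8.1.3.1, algorithm | DOOR at Day 8 | none stated |
| SAP 8.1.3.1, closing text | none stated | primary |
| Table 26 footnote a (IPW column); addendum Tables 14 and 15 | greatest reduction by Day 8 | no primary label |

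Table 28 has Day 8 rows and separate Maximum rows, and its footnote defines Maximum as the greatest reduction by Day 8. Read literally, the algorithm's outcome is not the endpoint.

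**2. The planned interval.** Protocol 10.2 gives 51% to 89% for a true DOOR probability of 70% with 20 per arm. The Wilcoxon-Mann-Whitney null variance is (n1 + n2 + 1)/(12 n1 n2) = 41/4800, so SE = 0.0924. The normal quantile gives 0.70 ± 1.96 × 0.0924 = 51.9% to 88.1%; the t quantile on 38 df gives 51.3% to 88.7%. The figure reproduces. On the normal version, an estimate must exceed about 0.50 + 0.181 = 0.681 to meet the rule.

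**3. Weighted against unweighted.** The SAP 8.1.3.1 pseudocode has treatment as its only predictor. Each subject's fitted probability is then the arm's completion proportion, so every pair has the same weight w = 1/(π1 π2). The estimate is Σ(w × indicator)/Σw, in which w cancels, leaving the unweighted mean. Over 2,000 simulated data sets the largest difference was 7e-16, which is rounding error. With the same outcome variable, the point estimates can differ only if other covariates enter, which the (X, Z) notation allows. The intervals can differ because the SAP does not say how the weights enter the Halperin variance.

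**4. Day 8 against greatest reduction.** The documents give no SD or time course, so these are assumptions: per-sample SD of 0.5, 0.75 or 1.0 log10, independent errors, no related SAE, and post-dose samples on Day 1 post-infusion and Days 2, 5 and 8. True log10 reductions at those four times were 1/1/1/1 (sustained), 0.5/1.5/1/0.25 (transient) and 0/0.25/0.75/1.25 (late), with 400,000 subjects per arm. The approximate lower limit in brackets is the probability minus 0.181.

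| Effect | SD | DOOR at Day 8 | Greatest reduction |
|---|---|---|---|
| None | all three | 0.500 | 0.500 |
| Sustained | 0.5 | 0.713 (0.532) | 0.813 (0.632) |
| | 0.75 | 0.671 (0.490) | 0.744 (0.563) |
| | 1.0 | 0.639 (0.458) | 0.690 (0.509) |
| Transient | 0.5 | 0.532 (0.351) | 0.833 (0.652) |
| | 0.75 | 0.534 (0.353) | 0.744 (0.563) |
| | 1.0 | 0.530 (0.349) | 0.682 (0.501) |
| Late | 0.5 | 0.785 (0.604) | 0.764 (0.583) |
| | 0.75 | 0.723 (0.542) | 0.687 (0.506) |
| | 1.0 | 0.679 (0.498) | 0.638 (0.457) |

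A second set of assumptions used SD 0.6 to 0.9. A transient effect of 1.2, 0.8 and 0.2 log10 on Days 2, 5 and 8 gave 0.53 at Day 8 against 0.66 to 0.73. A sustained 1-log10 effect gave 0.65 to 0.70 against 0.68 to 0.76.

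**5. Completeness.** If 10% of samples are missing independently at each visit (assumed) and baseline is present, Day 8 DOOR is missing in 20 × 0.1 = 2 subjects per arm of 20. Greatest-reduction DOOR is missing in 20 × 0.1^4 = 0.002. Independence is optimistic: the addendum reports 3 of 32 Stage 2a subjects undetectable at baseline and 2 at every later time point, so 5 of 32 had no DOOR when undetectable was treated as missing. The two indicators still differ.

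**The case against.** The strongest reply is that the intended outcome is clear. Footnote a, attached to the weighted column of Table 26 and repeated in addendum Tables 14 and 15, specifies the greatest reduction. Both tipping-point tables do too. The SAP also uses the Day 8 phrase loosely: 8.2.4 says "Analysis of the primary DOOR endpoint at Day 8 will be presented by subgroup", and Table 29 and addendum Tables 18 and 19 have Day 8 in their titles, yet their footnotes score the greatest reduction. This stands. A reader might infer that the SAP has moved the primary endpoint to Day 8; the documents do not support that. What they contain is an instruction in the algorithm that contradicts the shell it feeds.

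A reader might also infer that the two Table 26 columns must give different answers. Under the printed model, scored on one variable, their point estimates are the same.

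Two smaller inferences also fail. SAP 4.5 says "Sputum collection for measuring colony counts will occur at baseline and at follow-up visits occurring on Days 2, 5, 8, and 30", which omits the Day 1 post-infusion sample in the DOOR tables. That sample is taken at the Baseline/Dosing visit, so 4.5 can be read as a list of visits, and including the sample lowered the simulated probability by only 0.01 to 0.02. The Figure 12 note, "This figure will have one panel for Day 2, Day 5, and Day 8", has no Maximum panel, but Table 31 gives those results.

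Finally, protocol 10.1 and SAP 6.8 disclaim formal testing of the primary endpoints. The SAP nevertheless states a superiority rule, so the result it applies to must be identified.

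**Conclusion.** The point holds as two specification defects. First, the 8.1.3.1 algorithm names an outcome that contradicts the endpoint, the 8.1.3 list and footnote a of Table 26. Second, IPW is both sensitivity and primary, with the superiority rule on both columns and no resolution in the addendum.

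The size depends on how the conflict is resolved and on assumptions the documents cannot confirm. Correct scoring with the treatment-only model leaves the point estimate unaffected by the choice of column. Literal Day 8 scoring can move it either way: about 0.53 against 0.66 to 0.83 for a transient effect, 0.03 to 0.10 lower for a sustained effect, and 0.02 to 0.04 higher for a late one. Correlated visit errors would narrow these gaps.

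A reader might infer that Day 8 scoring reverses the superiority conclusion. Under the planning interval it does so in some scenarios but not in all: in every late-effect case the two scorings agree on the rule, and at 0.66 in the transient range the lower limit is about 0.48, so both fail. That interval is also not the Halperin interval planned for the analysis. A reversal is possible; it is not established.

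**What to change.** - In SAP 8.1.3.1, replace the Day 8 outcome with DOOR based on the greatest reduction by Day 8 + 3 (the Maximum rows), and define the completeness indicator on that variable.
- Have the sponsor state once whether the weighted or unweighted estimate is primary. Align SAP 6.5, 8.1.3, 8.1.3.1, Table 26 and addendum Table 14, and attach the superiority footnote to that column only. Which one to choose is the sponsor's decision.
- Name the missingness covariates, or state that treatment is the only one, and say how the weights enter the Halperin interval.
- Tidy the Day 8 wording in 8.2.4 and in the titles of Table 29 and addendum Tables 18 and 19 to match their footnotes.

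The cost is SAP wording and table labels, with no new data. The blinded statistician should make the change before the final analysis.
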